### **5. Material and Methods**

This is an international prospective cohort study. Consecutive patients will be included.

#### ***Variables of interest***

- Center ID
- Patient ID
- Age (at surgery)
- Premenopausal/Postmenopausal
- Genetic risk factors (BRCA1, BRCA2, ATM, CHECK2, PALB2, PTEN, TP53, etc. )
- Personal risk factors (tobacco smoke, alcohol, physical inactivity, substance abuse, Obesity, etc.)

- Comorbidity (high blood pressure, DM, chronic lung disease, deficiency anemias, kidney disease and failure, weight, height, BMI, etc. )
- Side (Right-Left)
- Objective examination axillary (palpable/not palpable)
- Mammography (date, nodule or microcalcifications, size in mm)
- Ultrasound breast (date, size in mm)
- Ultrasound axillary lymph nodes (negative/doubtful)
- Cytology or histology of doubtful axillary lymph node (yes/no)
- MRI (YES/NO)
  - Date, size in mm
- Unicentric/multifocal/multicentric
  - By mammogram, US, MRI
- Breast core biopsy Histological:
  - Date
  - Histotype (NST, lobular, other type)
  - Grade (1,2,3)
  - ER: %
  - PgR: %
  - Her2 0, 1+, 2+(FISH/SISH/ISH no amplified), 2+(FISH/SISH/ISH amplified)  
3+
  - Ki67: %
- Date of surgery
- Type of breast surgery (Lumpectomy, oncoplastic surgery (round block, mammoplasty)
- Definitive histological result:
  - pT (mm)
  - Foci (u, m)
  - Histotype (NST, lobular, invasive + DCIS, other type)
  - Grade (1,2,3)
  - ER: %
  - PgR: %
  - Her2 0, 1+, 2+(FISH/SISH/ISH no amplified), 2+(FISH/SISH/ISH amplified)  
3+
  - Ki67: %

- RT (yes/no)
  - PBI (yes/no)
    - Date (start/end)
    - If yes, type (intracavitary brachytherapy, interstitial brachytherapy, external beam radiation treatment (EBRT), single fraction intraoperative radiation (IORT) )
    - Gy
    - number of fractions
  - WBI (yes/no)

If yes:

- Date (start/end)
- Type (VMAT, breath holding, IMRT)
- Gy
- Number of fractions
- Boost dose (yes/no)
  - If yes, Gy
  - If yes, how many fractions
- Adjuvant endocrine therapy (yes/no)
  - Type of endocrine therapy (tamoxifen, Letrozole, exemestane, anastrozole, other SERD)
- Adjuvant CT (yes/no)

Follow-up

- Date of last follow-up
- Recurrence: yes/no
- Type of recurrence: local/regional/locoregional/synchronous (regional + distant, local + distant, locoregional + distant)
- Date of recurrence
- Deceased: yes/no
- Date of death
- Cause of death

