Other international trials have backed up these findings. Both the NAUTILUS (4) trial and the INSEMA (5) trial confirmed that management of patients with N0 on ultrasound can be carried out without axillary surgery, leading to improved survival outcomes and fewer complications. Likewise, omission of axillary surgery was reported to be both safe and improve health-related quality of life in the IIT 2015-06 Chung-SNBO trial(6) in South Korea and the BOOG 2013-08 study (7) in the Netherlands. The totality of the evidence from these studies suggests that in early-stage breast cancer, the minimally invasive approach with omission of sentinel lymph node biopsy can be a suitable solution that improves postoperative outcomes for patients.

Axillary ultrasound (AUS) is the method of choice worldwide to assess lymph node involvement in patients with known or suspected breast cancer.(8) With advances in imaging techniques, the accuracy of AUS to predict axillary status with or without node biopsy has increased significantly. According to the literature, US can be highly specific if morphologic characteristics are used, with a sensitivity ranging from 26% to 76% and a specificity of 88%–98% for nonpalpable metastatic lymph nodes. (9) The accuracy of AUS can be improved with image guided biopsy.

With the publication of the SOUND and the INSEMA trial, several questions have been raised related to the selection of adjuvant treatment in those patients with omitted SLN.

The changing in clinical practice after the publication of these trials are being implemented and, in some Institutions, patients with a negative clinical exam and negative axillary ultrasound, postmenopausal, age  $\geq 50$  years, with grade 1–2, ER positive  $> 10\%$ , T1, non-lobular invasive breast cancers and a Ki-67  $< 20\%$  , no longer require SLNB. (10)

This group of patients are the ones who most benefit from PBI, so the dilemma is whether patients who comply with the selection criteria for these trials can be treated with PBI considering that the SOUND trial included only 10% of patients treated with PBI.

Looking at the data in the SOUND trial, adjuvant radiotherapy and hormonal treatment are administered for most of the patients. Precisely, about 98% took hormone therapy, and 98% of patients underwent postoperative radiotherapy. Among these, 10% underwent partial breast irradiation (PBI), while the remaining portion got whole breast irradiation (WBI). (3)

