### Secondary endpoints

Evaluation of different type of radiation therapy

Evaluation of different type of systemic treatment

Evaluation of outcomes based on histologic stage and subtype

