#### **Statistical analysis**

A sample size calculation was performed to determine the number of participants required for a non-inferiority study comparing the experimental group to the general population. The reference axillary recurrence rate was set at 0.3% based on population data, while the expected recurrence rate in the experimental group was 1.0%, as reported in published studies. A significance level of 5% and a statistical power of 80% were used. The analysis determined that 744 participants were required. To account for potential dropouts and exclusions, the sample size was increased by 10%, resulting in a final adjusted sample size of 827 participants.

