## **6. Registration and therapy**

All patients with histologically confirmed invasive breast cancer and a negative axillary US who are candidates for omitting SLN biopsy or any axillary surgery will be informed about the possible participation in the study. The inclusion and exclusion criteria are verified by the investigator and written informed consent is obtained from the patient. Surgical treatment, pathological assessment and postoperative locoregional and systemic therapy should be conducted according to institutional and national standards. Since the OXYGENATE study is a non-interventional trial, the study sites do not deviate from their own institutional protocol at any timepoint. The follow up on patient status is conducted yearly during the first 5 years after surgery.

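### The definitive histotype list mixes invasive type with presence of DCIS, so its codes overlap and the definitive invasive type can go unrecorded

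*Protocol*

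**What the plan says.** Under Variables of interest in Section 5, the protocol asks for histotype twice. At core biopsy the list is "Histotype (NST, lobular, other type"; at definitive histology it is "Histotype (NST, lobular, invasive + DCIS, other type". Grade, ER, PgR, HER2 and Ki67 are separate items at both time points. No separate item records DCIS, and the protocol does not say whether the histotype field takes one answer or several.

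Section 3 gives as a secondary endpoint "Evaluation of outcomes based on histologic stage and subtype", without defining subtype. Section 6 describes the population approached as "All patients with histologically confirmed invasive breast cancer and a negative axillary US". The Background cites a profile used at some institutions to omit sentinel node biopsy, which is limited to "T1, non-lobular invasive breast cancers". The eligibility criteria in Section 4 set no histotype restriction, so lobular tumours can enter.

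**The concern.** The definitive list puts two properties into one set of codes: which invasive type the tumour is, and whether DCIS accompanies it. The codes are therefore not mutually exclusive, and the DCIS code carries no invasive type.

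At stake is any analysis of outcome by histotype. If some centres enter an NST tumour with DCIS as NST and others use the DCIS code, the NST group differs in composition by centre. Lobular tumours can leave the lobular group in the same way, and the DCIS group becomes a mixture of types. Lobular versus non-lobular is a natural question for this registry, given the profile quoted in the Background and the open eligibility. This is a matter of what is collected: an analysis plan can regroup codes but cannot restore a definitive type that was never entered.

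**Working it through.** No figure in the protocol depends on this item, so there is nothing to reproduce. The check is to set the two lists against the tumours that can occur. The last column assumes that the biopsy sampled the same type.

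| Tumour at surgery | Definitive codes that fit | Core-biopsy codes that fit |
|---|---|---|
| NST, no DCIS | NST | NST |
| NST with DCIS | NST; DCIS code | NST |
| Lobular, no DCIS | lobular | lobular |
| Lobular with DCIS | lobular; DCIS code | lobular |
| Other type, no DCIS | other | other |
| Other type with DCIS | other; DCIS code | other |

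1. Section 6 makes every patient invasive, so the word invasive in the fourth code separates no one. The code conveys only that DCIS is present.
2. Every tumour with DCIS fits two definitive codes and one core-biopsy code.
3. If one answer is allowed, entering the type loses the DCIS component, and entering the DCIS code loses the definitive type. If several answers are allowed, both can be kept, but nothing tells sites to tick both.
4. For a tumour under the DCIS code, the core-biopsy type is still on record. It fails as a substitute where the core result is missing or differs from the surgical specimen.

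For scale only, let N be the planned evaluable number (744, Statistical analysis section), d the share of tumours with DCIS, c the share of those entered under the DCIS code, and m the share of these whose core type is missing or differs from the definitive type.

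- Patients who fit two codes: N × d
- Patients with no definitive type recorded, under single choice: N × d × c
- Patients whose true type is recorded nowhere: N × d × c × m

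The protocol gives none of d, c or m. With d assumed between 20% and 80%:

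- 744 × 0.20 = 149
- 744 × 0.40 = 298
- 744 × 0.60 = 446
- 744 × 0.80 = 595

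These count patients who fit two codes. They are upper limits for the second and third quantities, reached only if c = 1 and, for the third, m = 1 as well.

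**The case against.** The strongest reply is that Section 5 is a list of variables and not an eCRF codebook. The form is not shown, and single choice is nowhere stated. Some bracketed lists in the same section clearly allow several answers: comorbidities, risk factors, and the whole-breast technique list, where breath holding can accompany a planning technique. This stands, and it makes the loss of type conditional. Against it, grade and HER2 under the same pathology heading have the same format and take one answer, so single choice is a natural reading; if several answers are meant, the protocol should say so.

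Three stronger readings are tempting, and the protocol does not support them.

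- A reader might infer that the invasive type is hidden for every tumour with DCIS. It is not: a site may still enter NST or lobular, and the core-biopsy type is recorded.
- A reader might infer that the subtype endpoint is misclassified. This is a risk only. Subtype is undefined, and if it means receptor-based subtype, the separate receptor and Ki67 items serve it fully.
- A reader might infer that biopsy and final histotype cannot be cross-tabulated. A 3-by-4 table can be made. Only agreement within the DCIS column cannot be read off, and no endpoint asks for it.

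It is also fair to say that the lobular profile is Background text on a decision about sentinel node biopsy, for which the core-biopsy type is the natural source, and that axillary events will be few. At the expected 1.0%, 744 × 0.010 = 7.4 events. If 10% of tumours were lobular (an assumption), 74 patients would contribute about 0.7 of them. Miscoding would hardly change a comparison of axillary recurrence by histotype, which is weak in any case. Invasive disease-free survival would have more events, but the protocol gives no rate for it.

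**Conclusion.** The point holds as a defect in a stated code list. The definitive histotype codes overlap, mix two properties and differ from the core-biopsy codes. If the field takes one answer, tumours entered under the DCIS code have no definitive invasive type, with the biopsy type as a partial backup, and coding may vary between centres. A histotype-based analysis of the secondary endpoint can then be misclassified.

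The size cannot be established from the protocol; the 149 to 595 patients are an upper limit under an assumed DCIS share. The conclusion rests on the table of codes and on the single-choice reading, and not on that range. Receptor-based subtype, both primary endpoints and the sample size are untouched. The correction is modest but worth making, because the loss is hard to repair later and cheap to prevent now.

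**What to change.** In Section 5 and the eCRF, replace the definitive histotype item with two:

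- invasive histotype: NST / lobular / mixed / other, one answer;
- associated DCIS: yes / no.

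Use the same invasive-type codes at core biopsy, and base any histotype analysis on the definitive invasive type. State in Section 3 whether subtype means histotype, receptor-based subtype or both.

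The cost is one extra eCRF field and short edits to the protocol. The present list already presumes that sites can report both type and DCIS, so no new source information is needed. Section 7 says only that use of the REDCap platform has been requested, so the form may still be open to change. If patients have already been entered, sites would have to be queried for the invasive type of those under the DCIS code.

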## **3. Study aims**

### Primary endpoint

Evaluation of the 3-year axillary recurrence rate

Evaluation of the 5-year invasive disease-free survival (iDFS)

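### The protocol's variable list has no field for HER2-directed or other targeted therapy, nodal irradiation, or axillary site of recurrence, although stated endpoints rest on them

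*Protocol*

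**What the plan says.** Section 3 (Study aims) lists "Evaluation of the 3-year axillary recurrence rate" as a primary endpoint, alongside 5-year invasive disease-free survival. Its secondary endpoints include "Evaluation of different type of radiation therapy" and "Evaluation of different type of systemic treatment". The Background (section 1) also names radiotherapy and systemic treatment as the focus of the registry.

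Section 5 (Variables of interest) is the only data specification in the protocol:

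- **Radiotherapy.** RT yes/no. Partial-breast irradiation has dates, technique, Gy and fractions. Whole-breast irradiation has dates, "Type (VMAT, breath holding, IMRT"), Gy, fractions and boost.
- **Systemic treatment.** Endocrine therapy yes/no with "Type of endocrine therapy (tamoxifen, Letrozole, exemestane, anastrozole, other SERD"), and "Adjuvant CT (yes/no").
- **HER2.** Recorded at core biopsy and again at definitive histology, as "Her2 0, 1+, 2+(FISH/SISH/ISH no amplified), 2+(FISH/SISH/ISH amplified") and 3+.
- **Recurrence.** Yes/no, date, and "Type of recurrence: local/regional/locoregional/synchronous (regional + distant, local + distant, locoregional + distant").

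Sections 4.1 and 4.2 exclude no HER2 category and do not mention nodal irradiation. Section 6 leaves postoperative locoregional and systemic treatment to local and national practice. Section 7 places data capture in a REDCap form, which is not reproduced.

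**The concern.** In a registry, what is not recorded prospectively cannot be analysed later, and no statistical analysis plan can repair that. Three items tied to stated endpoints are absent from the list.

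1. **HER2-directed and other non-endocrine targeted therapy.** HER2-positive patients can enter and their status is captured, but the treatment aimed at that status is not. For them the type of systemic treatment would be only partly described.
2. **Regional nodal or axillary irradiation.** No patient has axillary surgery, so radiation to the axilla would be local treatment of the site where the primary event occurs. Without a field for it, breast-only and breast-plus-nodal irradiation look the same when axillary recurrence is described by type of radiotherapy.
3. **Axillary site of recurrence.** The primary event has no code of its own. It would be entered as regional, locoregional or one of the synchronous combinations, and those labels can also cover nodal sites outside the axilla.

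At stake is how completely the stated endpoints can be described and interpreted.

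**Working it through.** **Step 1: endpoints against fields.**

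| Stated aim (section 3) | What section 5 records | What is not listed |
|---|---|---|
| Type of systemic treatment | Endocrine yes/no and agent; chemotherapy yes/no | Anti-HER2 or other targeted therapy |
| Type of radiotherapy | Partial- or whole-breast, technique, Gy, fractions, boost | Whether nodal regions were treated |
| 3-year axillary recurrence | Local, regional, locoregional, synchronous | Whether the axilla was involved |

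Open-ended wording (etc.) appears only under genetic risk factors, personal risk factors and comorbidity, so it does not extend the treatment or recurrence items. The yes/no fields for radiotherapy and chemotherapy identify neither a nodal target nor a targeted agent.

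**Step 2: the denominator.** The Statistical analysis section gives 744 patients, with rates of 0.3% (reference) and 1.0% (expected), 5% significance and 80% power. A two-sided one-sample normal approximation reproduces it:

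n = [1.960 × √(0.003 × 0.997) + 0.842 × √(0.010 × 0.990)]² / (0.010 − 0.003)² = 743.97, so 744.

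Allowing for 10% loss, 744 / 0.9 = 826.7, so 827, as stated. The point here does not depend on this calculation; 744 is used only as a denominator.

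**Step 3: size of the targeted-therapy gap.** The protocol gives no HER2-positive share. Assuming 5% to 15%:

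- 744 × 0.05 = 37.2
- 744 × 0.15 = 111.6

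Up to about 37 to 112 patients could have an incomplete systemic-treatment record.

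**Step 4: how few primary events there are.** Expected axillary events are 744 × 0.010 = 7.44. One event assigned to the wrong site moves the rate by 1/744 = 0.13 percentage points, which is about 13% of 1.0% (1/7.44). The exact (Clopper-Pearson) 95% interval for 7/744 is 0.38% to 1.93%.

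**Step 5: can a direction be given for nodal irradiation?** Let a share s be irradiated, let their underlying risk be r times that of the others, and let irradiation prevent a fraction e of their axillary events. If 1.0% is taken as the rate without nodal irradiation (an assumption, since the protocol does not give the irradiation mix behind it), the pooled rate is

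1.0% × [(1 − s) + s × r × (1 − e)].

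With assumed s = 30% and e = 50%:

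- r = 1: 1.0% × (0.70 + 0.30 × 0.5) = 0.85%
- r = 2: 1.0% × (0.70 + 0.30 × 1.0) = 1.00%
- r = 3: 1.0% × (0.70 + 0.30 × 1.5) = 1.15%

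At r = 2 and e = 50% the result is 1.0% for any s. The rate can fall, stay or rise depending on who is selected for irradiation, and the protocol gives none of s, r or e.

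**The case against.** **The list may not be exhaustive.** It is headed as variables of interest, and the electronic form is not shown. This stands as a limit: the point concerns the list as written, and whether data will actually be lost is unknown. If the form already has the items, the protocol only needs to be aligned with it.

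**The radiotherapy question is partial- versus whole-breast irradiation.** The Background frames it so, and section 5 records that contrast well. Nodal irradiation is never mentioned. A reader might infer that the comparison of the two techniques is confounded by unrecorded nodal treatment. The documents do not establish this. They show only that locoregional therapy follows local practice, so a difference between the groups is possible but not demonstrated.

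**The effect on the primary rate is not shown.** A reader might also infer that unrecorded nodal irradiation flatters the pooled axillary rate. Step 5 shows that the direction depends on quantities the protocol does not give. The pooled rate is still a valid real-world figure. With about seven expected events, covariate adjustment is unrealistic even with the field in place, and confounding by indication would remain.

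**This is only a wish for more variables.** That does not stand. A list that records breath holding, boost fractions and the endocrine agent is not a deliberately minimal dataset, and the missing items serve endpoints the protocol itself names.

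**Conclusion.** The point holds for the list as written. The clearest gap is targeted therapy: HER2-positive disease is eligible and its status is recorded, but the treatment is not, so the systemic-treatment endpoint is incomplete for those patients. The size, up to 37 to 112 of 744, rests wholly on the assumed 5% to 15% share.

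The nodal-irradiation gap is one of description: whole-breast irradiation with and without nodal fields cannot be told apart when axillary recurrence is reported by type of radiotherapy. The recurrence coding leaves the primary axillary event without separate identification, which matters because each event is worth about 0.13 percentage points.

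Neither bias in the pooled axillary rate nor a need for covariate adjustment is claimed. Outcomes by HER2, ER and grade, and by the radiotherapy and systemic items already listed, can still be tabulated. This is a low-cost improvement to make before data accumulate, not a defect that stops the registry.

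**What to change.** Add three items to section 5, Variables of interest, and to the electronic form if they are not already there:

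- anti-HER2 or other targeted therapy (yes/no; if yes, agent);
- regional nodal or axillary irradiation (yes/no), which is enough for descriptive use;
- within type of recurrence, axilla involved (yes/no).

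State that axillary recurrence and type of treatment will be described by these fields, without a claim of adjustment.

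The cost is a few more data-entry items per patient, taken from treatment and follow-up records that the sites already hold. No visit, procedure or change in treatment is needed. Recovering the same items later across international sites would be harder.

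### The follow-up fields cannot separate an in situ from an invasive breast recurrence, and lack other items needed for 5-year invasive disease-free survival, one of the two primary endpoints

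*Protocol*

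**What the plan says.** Protocol section 3 (Study aims) lists two primary endpoints: "Evaluation of the 3-year axillary recurrence rate" and "Evaluation of the 5-year invasive disease-free survival (iDFS", the latter with its abbreviation in brackets. It gives no list of the events that make up iDFS, and no other section does.

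The data to be collected are in section 5, under Variables of interest. The follow-up part consists of the date of last follow-up, "Recurrence: yes/no", the type of recurrence, the date of recurrence, and death with its date and "Cause of death". The type item reads "Type of recurrence: local/regional/locoregional/synchronous (regional + distant, local + distant, locoregional + distant" and is purely anatomical.

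The only field that mentions in situ disease is "Histotype (NST, lobular, invasive + DCIS, other type", and it belongs to the definitive histology of the primary tumour. Section 6 confirms that the index tumour is invasive ("All patients with histologically confirmed invasive breast cancer and a negative axillary US") and sets the schedule: "The follow up on patient status is conducted yearly during the first 5 years after surgery".

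**The concern.** The word invasive in the endpoint's name requires that invasive and in situ breast events be separated. Section 4.1 admits candidates for breast-conserving surgery, so breast tissue remains and an in situ recurrence in that breast is possible. A site that sees one can enter it as a local recurrence or leave it out, and the protocol does not say which. Once entered as local, it looks the same in the data as an invasive recurrence.

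At stake is whether the figure reported as 5-year iDFS is the quantity named in section 3, and whether it can be set beside iDFS from the trials that motivate the registry. Sites follow their own institutional protocols, so recording may also differ between centres.

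The gap is not confined to in situ disease. A distant recurrence without local or regional disease fits none of the listed types. Contralateral breast cancer and second primary malignancy have no field, although the Background reports both as outcomes of the SOUND trial.

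**Working it through.** **1. The plan's own figure.** The Statistical analysis text gives 744 patients, and 827 after a 10% allowance. A one-sample test of a proportion with p0 = 0.003, p1 = 0.010, two-sided 5% and 80% power gives

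n = [1.960 × √(0.003 × 0.997) + 0.842 × √(0.010 × 0.990)]² / (0.010 − 0.003)² = 743.97, so 744.

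Then 744 / (1 − 0.10) = 826.7, so 827. Both figures reproduce. They rest on axillary recurrence alone, so nothing below changes them.

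**2. Endpoint against fields.** The first column lists events that an iDFS definition may have to include or exclude. The protocol itself does not list them.

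| Event | What the listed fields allow |
|---|---|
| Invasive breast recurrence | Yes, local, date |
| In situ breast recurrence | Yes, local, date: identical to the row above |
| Regional recurrence | Yes, regional, date |
| Distant recurrence alone | Yes and date, but no type fits |
| Contralateral breast cancer | No field; could be entered as a recurrence or omitted |
| Second primary malignancy | No field; visible only if it is the cause of death |
| Death | Date and cause |

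The first two rows cannot be separated by any analysis of these fields.

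**3. Size of the in situ part.** Inputs: 744 patients (Statistical analysis); 1% local breast relapse in the whole SOUND cohort (Background); an in situ share of 10-30%, which is an assumption because the protocol gives none.

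- Local relapses: 744 × 0.01 = 7.44.
- In situ only: 7.44 × 0.10 = 0.74, to 7.44 × 0.30 = 2.23.
- On the iDFS scale: 0.74 / 744 = 0.1 percentage points, to 2.23 / 744 = 0.3 percentage points.

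**4. Sensitivity.** The Background does not say whether its 1% includes in situ lesions. If it is invasive only, and in situ lesions are 10-30% of all local relapses, they come on top: 7.44 × 0.10/0.90 = 0.83 to 7.44 × 0.30/0.70 = 3.19 events, or 0.1 to 0.4 points. The registry takes any age, cT1-2 and multifocal or multicentric disease, so its local relapse rate may differ. With an assumed 3% local relapse and an assumed in situ share of 10-40%, the count is 744 × 0.03 × 0.10 = 2.2 to 744 × 0.03 × 0.40 = 8.9 events, or 0.3 to 1.2 points.

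**5. The other gaps, on the same scale.** The Background gives 1% contralateral breast cancer and about 3% other malignancies. On 744 patients that is 7.4 and 22.3 events, 29.8 together. If the iDFS definition counts these and sites have nowhere to enter them, iDFS is overstated by up to about 1 point (contralateral only) or 4 points (both). In situ events counted by default act the other way.

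**The case against.** Four stronger readings are tempting, and the protocol supports none of them.

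- *In situ recurrences would count as iDFS events.* This needs an event definition or a coding instruction, and there is neither. What can be said is that such a lesion, if entered as local, cannot be identified and removed.
- *iDFS would be biased downward.* That is the direction of the in situ part taken alone. Missing contralateral and second-primary events, if they belong to the definition, push the other way and could be more numerous (step 5 of the working).
- *The analyst could compute plain disease-free survival instead.* A version that counts contralateral or second primary cancers cannot be computed from the list either.
- *The comparison of partial with whole breast irradiation would be distorted.* The secondary endpoints mention only an evaluation of radiotherapy types. No contrast between the two and no local-event analysis is stated, and about 7 local events split across radiotherapy groups would say little in any case.

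It can also be said that the effect is minor, that no iDFS target, margin or test is stated against which to call it material, and that a list headed Variables of interest may not be the final eCRF, which is not shown. The first two are right and limit the weight of the point. The third lowers certainty about what will be collected. But the list is detailed, down to the number of boost fractions, and the follow-up items carry no open-ended etc., unlike the risk-factor and comorbidity items. Nor can the matter be left to a statistical analysis plan: it can define iDFS, but it cannot supply pathology that was not recorded.

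**Conclusion.** The point holds as a data-capture gap: from the fields the protocol lists, 5-year iDFS cannot be derived as invasive disease-free survival. The in situ part alone is probably small, 0.1 to 0.3 percentage points under 1% local relapse and an assumed 10-30% in situ share, and up to 1.2 points under the less favourable assumptions in step 4. The net direction of error in iDFS is not determined, because the protocol does not define the events and the same list lacks a distant-only category and contralateral and second-primary items. The axillary recurrence endpoint and the 744 and 827 patients are not affected. The point is worth acting on because the remedy is cheap now, whereas the missing pathology would later have to be retrieved from many centres.

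**What to change.** In section 5, Follow-up:

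- add, for each recurrence and with its own date, the pathology: invasive, in situ only, or not biopsied;
- add a category for distant recurrence alone to the type of recurrence;
- add dated items for contralateral breast cancer (with the same pathology options) and for second primary malignancy.

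In section 3, state which of these events, together with death, count towards iDFS, and how a recurrence without biopsy is handled. Count only invasive breast recurrences in iDFS and report in situ recurrences separately. The pathology item alone would not be enough, because iDFS would still be incomplete if contralateral or second primary cancers belong to it.

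The cost is a few eCRF items, filled from pathology reports and records of routine care, and a short event list in section 3. Section 7 says only that use of the REDCap platform has been requested, which suggests that the form can still be changed. Patient care and the sample size do not change.
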